9.4.2 Safety Analyses

All safety analyses will be based on the safety analysis set (see [Table 11](#)). Participants will be summarized by cohort. In addition, all study participants who are randomized to receive SC or IV placebo will be pooled as respective SC or IV placebo control groups, according to each part of the study.

The safety data, including AEs, injection-site reactions, reasons for withdrawal from study, laboratory data, ECG, concomitant medications, vital signs, and physical examination results will be listed and summarized descriptively. Marked abnormalities of laboratory data will be flagged. As appropriate, listings, summary tables and graphs (participant plot and/or mean plots) will be provided to describe safety and tolerability assessments.

Table 11 Safety Statistical Analysis Methods

| Endpoint | Statistical Analysis Methods |
|---------------------------|--|
| Adverse events | The original terms recorded on the eCRF by the Investigator for AEs will be coded by the Sponsor. AEs will be summarized by mapped term and appropriate thesaurus level. Frequency and severity of adverse events will be summarized. |
| Clinical laboratory tests | All clinical laboratory data will be stored on the database in the units in which they were reported. Laboratory test values will be presented in International System of Units (SI units) by individual outputs with flagging of abnormal results. Summary tables of absolute value and change from baseline over time will be displayed. Shifts in DAIDS grades v2.1 from baseline to the worst grade observed during treatment will be presented for selected laboratory parameters. For details on standard reference ranges and data transformation and the definition of laboratory abnormalities, see Appendix 4 . |
| Vital signs | Vital sign data will be presented with flagging of values outside the normal ranges and flagging of abnormalities. Mean changes from baseline and absolute value over time will be provided. |
| ECG data analysis | ECG data will be presented using appropriate outputs, as detailed in Section 9.4.2.1 . |
| Concomitant medications | The original terms recorded on the participants' eCRF by the Investigator for concomitant medications will be standardized by the Sponsor by utilizing a mapped term and appropriate drug dictionary level. Concomitant medications will be presented using appropriate outputs. |

Abbreviations: AE = adverse events; DAIDS = Division of AIDS; ECG = electrocardiogram; eCRF = electronic case report form; SI = Système International d'Unités.

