- n. PK samples will be collected at predose (within 2 hours prior to drug administration), then 1 hour (\pm 5 minutes), 4 hours (\pm 15 minutes), and 8 hours (\pm 30 minutes) postdose on Day 1 of the first and the last treatment periods.
- o. Samples will be collected at predose, then 4 hours and 8 hours postdose on Day 1 of the first and the last treatment periods.

Table 3 Schedule of Activities – Part 2

| Protocol Section | Cycle/Visit/Week | Screening | | Visits | | | | | | | | | | | | | Additional visits ^a | ET | Virological breakthrough |
|-------------------|---|----------------|--------------|-------------------|-------|----------------|-------|----------------|----------------|----------------|----------------|----------------|----------------|----------------|----------------|----------------|--------------------------------|----------------|--------------------------|
| | | Day | Day 0 to D-1 | Day 1 | Day 2 | Day 3 | Day 4 | Day 8 | Day 15 | Day 22 | Day 29 | Day 57 | Day 85 | Day 113 | Day 141 | Day 169 | | | |
| | Day | | | 0 | 24 | 48 | 72 | 168 | 336 | 504 | 672 | 1344 | 2016 | 2688 | 3360 | 4032 | every 56 days | | |
| | Time Relative (h) | | | 0 | 0 | 0 | 0 | ± 1 day | ± 1 day | ± 1 day | ± 3 days | ± 7 days | | |
| | Visit Window | | | | | | | | | | | | | | | | | | |
| | Assessments | | | | | | | | | | | | | | | | | | |
| Appendix 1 | Informed Consent | x | | | | | | | | | | | | | | | | | |
| 8.2.5 | Demography | x | | | | | | | | | | | | | | | | | |
| 5.2 | Eligibility | x | x | | | | | | | | | | | | | | | | |
| 8.2.5 | Medical History | x | | | | | | | | | | | | | | | | | |
| 8.2.1 | Complete physical Examination | x ^b | | | | | | | | | | | | | | | | | |
| 8.2.1 | Symptom directed physical examination | | | x ^{b, c} | x | x | x | x ^b | x | |
| 5.2, Appendix 4 | Blood Chemistry (Includes lipids and Cystatin C) | x | x | x ^c | x | | | x | x | x | x | x | x | x | x | x | x | x | x |
| 5.2, Appendix 4 | GLDH (exploratory) | | | x ^c | x | | | x | x | x | x | x | x | x | x | x | x | x | x |
| 5.2, Appendix 4 | Hematology | x | | x ^c | x | | | x | x | x | x | x | x | x | x | x | x | x | x |
| 5.2, Appendix 4 | Urinalysis | x | | x ^c | x | x | x | x | x | x | x | x | x | x | x | x | x | x | x |
| 5.2, Appendix 4 | Coagulation | x | | x ^c | x | | | x | x | x | x | x | x | x | x | x | x | x | x |
| Appendix 4 | C3, C4, and total hemolytic complements (CH50), CRP ^d | | | x ^c | | | | | | | | | | | | | | | |

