| 8.6 | Anti-Drug Antibody (ADA) ^m | | | | | x ^c | | | | x | x | x | x | x | x | x | x | x | x |
| 8.3.7 | NUC PK | | | | | | | | | | | | | | | | | | x |
| 8.7.4 | Cytokine/Chemokine profile and complement activation (SC5b-9) ^d | | | 3 ^h | x | x | x | x | x | x | x | x | x | x | x | x | x ^o | | |
| 8.7.4 | PBMC HBV-specific cellular immune response ^p | | | x ^c | | | | | | | x | x | x | x | x | x | x | x ^o | |
| 8.7.5 | Clinical Genotyping | | | | | x | | | | | | | | | | | | | |
| 8.7.4 | scRNAseq | | | x ^c | | | | | | | x | x | x | x | x | x | x | x ^o | |
| 8.9 | Research Biosample Repository (RBR) ^q | | | x ^c | | | | | | | x | x | x | x | x | x | x | x | x |
| 8.3 | Adverse Events | | | | | | x | | | | | | | | | | x | x | x |
| 6.5 | Previous and Concomitant Treatments | | | | | | x | | | | | | | | x | x | x | x | x |

Table 3 Schedule of Activities – Part 2 (cont.)

Abbreviations: ADA = anti-drug antibody; AE = adverse event; AFP = α -fetoprotein; AMA = antimitochondrial antibody; ANA = antinuclear antibody; ARFI = elastography/acoustic radiation force impulse; ASMA = anti-smooth muscle antibody; a-TPO = anti-thyroid peroxidase; CRP = C-reactive protein; ECG = electrocardiogram; ET = early termination; HAV = hepatitis A virus; HBcrAg = hepatitis B core-related antigen; HBeAg = hepatitis B e antigen; HBsAb = hepatitis B surface antibody; HBsAg = hepatitis B surface antigen; HBV = hepatitis B virus; HCV = hepatitis C virus; HDV = hepatitis D virus; HEV = hepatitis E virus; HIV = human immunodeficiency virus; MRI = magnetic resonance imaging; NUC = nucleos(t)ide analogue; PBMC = peripheral blood mononuclear cell; PK = pharmacokinetic; RBR = research biosample repository; SAE = serious adverse event; scRNAseq = single-cell RNA sequencing.

- a. If HBsAg value does not return to baseline level on Day 169, participants will come to the clinic for additional follow-up visits every 56 days until HBsAg value returns to < 0.1 log below baseline for two consecutive visits, or up to Day 393, whichever comes first.
- b. Weight and height will be collected during screening period. Weight will be collected in the following visits except Day 2, Day 3, and Day 4 visits.
- c. Assessments or sample collection will be performed at predose.
- d. Unscheduled sample for complement activation and CRP will be collected for suspected immune complex mediated adverse events and other events following Section 8.3.7.

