3. OBJECTIVES AND ENDPOINTS

The objectives and corresponding endpoints are provided in [Table 5](#).

Table 5 Objectives and Endpoints

| Objectives | Endpoints |
|--|--|
| Primary | |
| 
 • To assess the safety and tolerability: 
 ◦ following a single dose of RO7565020 administered subcutaneously (SC) or intravenously (IV) to healthy participants (Part 1a) and SC to virologically suppressed participants with chronic hepatitis B (CHB) (Part 2) ◦ following multiple doses of RO7565020 administered SC to healthy participants (Part 1b) and virologically suppressed participants with CHB (Part 3) | 
 • Frequency and severity of adverse events (AEs), including adverse events of special interest (AESI), serious adverse events (SAE), and treatment discontinuations due to AEs • Frequency of abnormal laboratory findings based on hematology, blood chemistry (including liver function tests), coagulation and urinalysis test results • Frequency of clinically significant abnormalities in ECGs and vital signs • Mean changes from baseline in vital signs (temperature, systolic and diastolic blood pressure, pulse rate, respiratory rate) over time |
| Secondary | |
| 
 • To investigate the serum pharmacokinetics of RO7565020: 
 ◦ following single-ascending doses of RO7565020 administered SC or IV to healthy participants (Part 1a) and SC to virologically suppressed participants with CHB (Part 2) ◦ following multiple doses of RO7565020 administered SC to healthy participants (Part 1b) and virologically suppressed participants with CHB (Part 3) | 
 • PK parameters of RO7565020: 
 ◦ Time to maximum concentration (t_{max}) ◦ Maximum serum concentration observed (C_{max}) ◦ AUC from Time 0 to time of last sampling point or last quantifiable sample, whichever comes first (AUC_{0-last}) ◦ AUC from Time 0 to infinity (AUC_{inf}) ◦ Terminal half-life ($t_{1/2}$) ◦ Volume of distribution (V_{ss}) and clearance (CL) (IV only) ◦ Apparent clearance (CL/F), apparent volume of distribution at terminal phase (V_z/F) (SC only) |

Table 5 Objectives and Endpoints (cont.)

| Objectives | Endpoints |
|---|---|
| Secondary (cont.) | |

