4.3 DURATION OF PARTICIPATION

The duration of each study period is described in [Table 7](#).

Table 7 Duration of Study Periods

| Study Part | Screening | Treatment period | In-clinic period | End-of-study visit*** |
|------------------------|--|------------------|---|--|
| Part 1a | Up to 28 days | Day 1 | Day -1 to Day 4 | 36 weeks after study treatment administration |
| Part 1b | Up to 28 days | Up to 169 days | Day -1 to Day 4, and 1 day after each administration for the following doses, including optional overnight stay* | 36 weeks after the final study treatment administration |
| Parts 2a and 2b | Up to 56 days (Pregnancy testing and liver function up to 14 days) | Day 1 | Day 1** to Day 4, including optional overnight stay* | 24 weeks after study treatment administration (If HBsAg does not return to baseline level at follow-up Week 24, will have additional follow-up visits until returns to <0.1 log below baseline for two consecutive visits, or up to 56 weeks postdose, whichever comes first.) |
| Part 3 | Up to 56 days (Pregnancy testing and liver function up to 14 days) | Up to 337 days | Day 1** to Day 4, and 1 day after each administration for the following doses, including optional overnight stay* | 24 weeks after last study treatment administration (If HBsAg does not return to baseline level at follow-up Week 24, will have additional follow-up visits until return to <0.1 log below baseline for two consecutive visits, or up to 56 weeks post the final dose, whichever comes first.) |

Abbreviations: ADA = anti-drug antibody; HBsAg = hepatitis B surface antigen;

PK = pharmacokinetic.

Note: Participants who permanently discontinue from the study (or study treatment) due to Sponsor's decision (e.g., Sponsor prematurely terminates the study) will undergo safety follow-up for 24 weeks or longer if considered needed by Sponsor on the basis of the emerging data. Every 4 weeks (\pm 3 days) in the first 12 weeks post-final dose, then every 12 weeks (\pm 7 days).

* For Part 1b, all participants will stay at the clinic overnight on Day 1 after each dose. Optional overnight stay at the clinic on Day 2 and Day 3 after the first dose, i.e., on Day 2 and Day 3, participants can either stay at the clinic overnight or can be discharged after completion of the assessments and return the next morning for the subsequent assessments, at the Investigator's discretion.

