8.3.1 Period and Frequency for Collecting Adverse Event and Serious Adverse Event Information

The method of recording, evaluating, and assessing causality of AEs and SAEs and the procedures for completing and transmitting SAE reports are provided in [Appendix 2](#).

Investigators will seek information on AEs at each participant's contact. All AEs, whether reported by the participant or noted by study personnel, will be recorded in the participant's medical record and on the Adverse Event eCRF as follows:

After informed consent has been obtained **but prior to initiation of study treatment**, only SAEs caused by a protocol-mandated intervention should be reported (e.g., SAEs related to invasive procedures such as biopsies). Any other AE should not be reported.

After initiation of study treatment, all AEs, regardless of relationship to study treatment, will be reported until the last scheduled follow-up visit.

Post-study AEs and SAEs: The Investigator is not required to actively monitor participants for AEs after the end of the AE reporting period, defined as their last scheduled follow-up visit.

However, if the Investigator learns of any SAE (including a death) or other AEs of concern that are believed to be related to prior treatment with study treatment at any

time after a participant has been discharged from the study, and the Investigator considers the event to be reasonably related to the study treatment or study participation, the Investigator must promptly notify the Sponsor. For the procedure of reporting, see [Appendix 2](#).

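### Part 2 adverse events are tabulated by cohort over follow-up that ends anywhere from Day 169 to Day 393 depending on HBsAg response, with no common window (minor)

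*Combined protocol and SAP*

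**What the plan says.** **Length of follow-up.** Note a to Table 3 (section 1.3) sets the trigger for further visits: "If HBsAg value does not return to baseline level on Day 169". These visits take place "every 56 days until HBsAg value returns to < 0.1 log below baseline for two consecutive visits, or up to Day 393". Table 7 (section 4.3) gives the same upper limit in weeks: participants "will have additional follow-up visits until returns to <0.1 log below baseline for two consecutive visits, or up to 56 weeks postdose".

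**AE collection.** Under section 8.3.1, after treatment starts, "all AEs, regardless of relationship to study treatment, will be reported until the last scheduled follow-up visit". Table 3 also marks AEs in the column for additional visits. The AE period therefore ends on a different day for different participants.

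**Analysis.** AE frequency and severity are primary endpoints (section 3, Table 5). Section 9.4.2 summarises participants by cohort. For AEs, Table 11 says only "AEs will be summarized by mapped term and appropriate thesaurus level. Frequency and severity of adverse events will be summarized". The safety set in Table 10 takes in every dosed participant without a time limit. Sections 9.3 to 9.5 give no cut-off day, no participant-time denominator and no separate summary of the extension.

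**Laboratory shift row.** Table 11 takes the worst DAIDS grade seen on treatment. Table 7 gives the Part 2 treatment period as Day 1.

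**The concern.** A cumulative count of participants with an event can only grow as observation lengthens. If one Part 2 cohort has more participants in extension than another, its all-follow-up AE frequency covers more time, and the planned table does not show this.

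The imbalance could be related to dose. Section 4.2.4 says the higher Part 2 doses aim at larger and longer-lasting HBsAg reductions, and an HBsAg level that stays down is what keeps a participant in follow-up. Part 2 has no placebo arm (section 4.2.2), so within Part 2 the other cohorts are the only concurrent comparison. What is at stake is how a primary safety table can be read. No test or error rate is involved.

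**Working it through.** **The plan's own figure.** Section 9.2 states at least an 80% chance of seeing one or more AEs, using 1 − (1 − p)^n:
- n = 5, p = 0.28 gives 80.65%.
- n = 6, p = 0.24 gives 80.73%.

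Both reproduce. They are detection thresholds with no time window attached, not expected incidences.

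**Time at risk, from Table 3.** Dosing is on Day 1, so days at risk are the visit day minus 1. The possible extension visits are Days 225, 281, 337 and 393.

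| Last visit | Days at risk | Ratio to Day 169 |
|---|---|---|
| Day 169 | 168 | 1.00 |
| Day 225 | 224 | 1.33 |
| Day 281 | 280 | 1.67 |
| Day 393 | 392 | 2.33 |

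The trigger (return to baseline, no tolerance stated) and the stop rule (less than 0.1 log below baseline at two consecutive visits) are different criteria. On the natural reading the earliest extended stop is Day 281 (Days 225 and 281 both qualify). It is Day 225 if a Day 169 value within 0.1 log, but not at baseline, counts as the first of the two visits.

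**What this could do to AE frequency (illustration only).** The documents give no expected incidence or late hazard, so both are assumed. Let p be the risk by Day 169, x the extra time divided by 168 days, and m the late hazard as a fraction of the early hazard. Then risk = 1 − (1 − p)^(1 + m·x).

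With p = 0.24:
- m = 0: 24% at any stop day.
- m = 0.25: 25.7% (Day 225), 27.4% (Day 281), 30.6% (Day 393).
- m = 1: 30.6% (Day 225), 36.7% (Day 281), 47.3% (Day 393).

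Other values of p, from m = 0.25 at Day 281 to m = 1 at Day 393:
- p = 0.10: 11.6% to 21.8%.
- p = 0.50: 55.5% to 80.2%.

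**In a cohort of 6 at p = 0.24.**
- None extended: 6 × 0.24 = 1.44 participants expected with the event.
- Three extended, m = 0.25, Day 281: 3 × 0.274 + 3 × 0.24 = 1.54.
- Three extended, m = 1, Day 393: 3 × 0.473 + 3 × 0.24 = 2.14.
- Binomial SD: √(6 × 0.24 × 0.76) = 1.05, so the shifts are about 0.1 and 0.7 SD.

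**Would a participant-time rate solve it?** The rate to Day 393 relative to the rate to Day 169 is (1 + 1.333m)/2.333. This is 1.00, 0.71, 0.57 and 0.43 for m = 1, 0.5, 0.25 and 0. The rate is neutral only under a constant hazard. If events cluster early, it makes the longer-followed cohort look safer.

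**The case against.** The case against giving this weight is substantial, and most of it stands.

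- **Nothing is decided on this table.** Section 9.1 plans no hypothesis tests and section 9.4 calls the summaries descriptive. Escalation rests on data from at least 28 days postdose (section 4.1.1.1). The stopping rules count treatment-related severe or serious reactions (section 4.1.1.3). By-timepoint laboratory, vital-sign and ECG tables are not cumulative. All of this stands.
- **The link to dose is a design aim.** The trigger has no stated tolerance. Read strictly, a small shortfall at Day 169 would extend follow-up at any dose, and extension could be common in every cohort. This stands.
- **Counting AEs until the drug effect wanes is legitimate.** Extended participants still have reduced HBsAg, so a late event may be a real effect. This stands, and is why late events should be displayed, not dropped.
- **Cross-cohort reading is not the stated basis for safety.** Section 4.2.2 relies on Part 1 for off-target safety and expects HBsAg-related AEs to be readily attributable. This lowers the weight of the point. The primary endpoint is still tabulated by cohort, and readers may compare the columns.
- **Listings suffice.** With 30 to 42 Part 2 participants (5 to 7 cohorts of 6), events after Day 169 can be picked out by hand. That is possible, but a period table does it directly.

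A reader might also infer that the laboratory shift table is inflated because extended participants give more samples. The documents do not support that. The shift is limited to the treatment period, which Table 7 gives as Day 1 in Part 2. Whether later samples enter depends on how that limit is read. What remains is a window that does not fit Part 2.

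**Conclusion.** The point holds, and its severity is minor. As written, the Part 2 AE table combines participants observed for 168 days with others observed for 224 or 280 up to 392 days. Which group a participant falls into depends on HBsAg response. A difference between cohorts in cumulative AE frequency could be dose-related, due partly to longer observation, or both, and the planned summary cannot show which.

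Only the 1.33 to 2.33 ratio comes from the documents. The effect on AE frequency, and which cohort would carry it, are unknown. It is nil if no AE risk persists after Week 24 or if extension is similar across cohorts. The 0.1 to 0.7 SD illustration rests on an assumed 24% risk, an assumed late hazard and half the cohort being extended.

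A reader might infer that higher-dose cohorts will show more AEs through longer observation alone. The documents do not support this. They contain no data on extension by dose or on late AE risk, and continuing drug activity is an equally possible cause of late events.

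**What to change.** In section 9.4.2, for Part 2:

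1. Add a by-cohort AE summary from dose through Day 169, named as the like-for-like display between cohorts.
2. Keep the all-follow-up AE summary.
3. Show events after Day 169 separately, with the number of participants still followed in each cohort and their follow-up duration.
4. In the laboratory shift row, replace the on-treatment window with a stated post-baseline window (dose through Day 169) and show later values separately.

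If Part 3 is run, the same AE display can be used within cohort, from first dose through Day 169 after the last dose. Table 4 note b has the same extension rule there. A participant-time rate should not replace the fixed window, because it is neutral only under a constant hazard.

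The cost is some wording and a few extra tables from data already collected, with no added visits or samples. The Day 169 cut does not equalise everything: early terminators will still have shorter follow-up.

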| Appendix 4 | Immunology (ANA, AMA, ASMA, a-TPO) | x | | | | | | | | | | | x ^{f,h} | | | | | | |
| Appendix 4 | Thyroid function tests | x | | | | | | | | | | | x ^{f,h} | | | | | | |
| Appendix 4 | Pregnancy Test ⁱ | x | x | | | | | | | | | | x ^{f,j} | | | | | | x |
| Appendix 4 | HAV, HCV, HIV, HBV | x | | | | | | | | | | | | | | | | | |
| 5.1.2 | Alcohol Use History | x | | | | | | | | | | | | | | | | | |
| 5.1.2, Appendix 4 | Alcohol, cotinine, and drugs abuse testing | x | x | | | | | | | | | | | | | | | | |
| 4.3 | Admission to Unit ^k | | x | | | | | | | | | | x | | | | | | |
| 4.3 | Discharge from Unit ^k | | | | x | | | | | | | | x | | | | | | |
| 4.3 | Ambulatory Visit ^k | | | | | x | | x | x | x | x | x | | x | x | x | x | x | x |
| 4.1 | Administration of Study Treatment | | | x | | | | | | | | | x | | | | | | |
| 8.5 | RO7565020 PK Sample(Serum) ^{l,m} | | 4 ⁿ | x | x | x | x | x | x | x | x | x | x ^f | x | x | x | x | x | x |
| 8.6 | Anti-Drug Antibody (ADA) ^m | | x ^f | | | | | x | x | x | x | x | x ^f | | | x | x | x | x |
| 8.7.4 | Cytokine/Chemokine profile and complement activation (SC5b-9) (serum) | | 3 ^o | x | x | x | x | x | x | x | x | x | x ^f | x | x | x | x | x | x |
| 8.3 | Adverse Events | | | | x | | | | | | | | | | x | | | | |
| 6.5 | Previous and Concomitant Treatments | | | | x | | | | | | | | | | x | | | | |

Table 2 Schedule of Activities – Part 1b (cont.)

| Protocol Section | Period/Visit/Week ^a | Last treatment period | | | | | | | | | | | | | ET |
|-------------------|---|-----------------------|----------------|----------------|----------------|----------------|----------------|----------------|----------------|----------------|----------------|----------------|----------------|----------------|----|
| | | Day 1 | Day 2 | Day 3 | Day 4 | Day 8 | Day 15 | Day 21 | Day 29 | Day 57 | Day 85 | Day 141 | Day 197 | Day 253 | |
| | Day ^b | | | | | | | | | | | | | | |
| | Time Relative (h) | 0 | 24 | 48 | 72 | 168 | 336 | 480 | 672 | 1344 | 2016 | 3360 | 4704 | 6048 | |
| | Visit Window ^b | 0 | 0 | 0 | 0 | ± 1 days | ± 1 days | ± 3 days | ± 7 days | ± 7 days | |
| | Assessments | | | | | | | | | | | | | | |
| Appendix 1 | Informed Consent | | | | | | | | | | | | | | |
| 8.2.5 | Demography | | | | | | | | | | | | | | |
| 5.1 | Eligibility | | | | | | | | | | | | | | |
| 8.2.5 | Medical History | | | | | | | | | | | | | | |
| 8.2.1 | Complete Physical Examination | | | | | | | | | | | | | | |

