| 8.5 | RO7565020 PK Sample ^{t,u} | 4 ^v | x | x | x | x | x | x | x | x | x | x | x | x | x | x |
| 8.6 | Anti-Drug Antibody (ADA) ^u | x ^f | | | x | x | x | x | x | x | x | x | x | x | x | x |
| 8.3.7 | NUC PK | | | | | | | | | | | | | | x | |
| 8.7.4 | Cytokine/Cytokine profile and complement activation (SC5b-9) (serum) ^p | 3 ^h | x | x | x | x | x | x | x | x | x | x | x | x ^w | | |
| 8.7.4 | PBMC HBV-specific cellular immune response (blood) ^x | x ^f | | | | | | x | | x | | | | x ^w | | |
| 8.7.5 | Clinical Genotyping | x ^f | | | | | | | | | | | | x ^w | | |
| 8.7.4 | scRNAseq (blood) | x ^f | | | | | | x | | x | | x | x | x ^w | | |
| 8.9 | Research Biosample Repository (RBR) ^y | x ^f | | | | | x | | x | | x | x | x | x | x | |
| 8.3 | Adverse Events | | | | | | x | | | | | | x | x | x | x |
| 6.5 | Previous and Concomitant Treatments | | | | | | x | | | | | x | x | x | x | x |

Table 4 Schedule of Activities – Part 3 (cont.)

Abbreviations: ADA = anti-drug antibody; AE = adverse event; AFP = α -fetoprotein; AMA = antimitochondrial antibody; ANA = antinuclear antibody; ARFI = elastography/acoustic radiation force impulse; ASMA = anti-smooth muscle antibody; a-TPO = anti-thyroid peroxidase; CRP = C-reactive protein; ECG = electrocardiogram; ET = early termination; FU = follow-up; HAV = hepatitis A virus; HBcrAg = hepatitis B core-related antigen; HBeAg = hepatitis B e antigen; HBsAb = hepatitis B surface antibody; HBsAg = hepatitis B surface antigen; HBV = hepatitis B virus; HCV = hepatitis C virus; HDV = hepatitis D virus; HEV = hepatitis E virus; HIV = human immunodeficiency virus; MRI = magnetic resonance imaging; NUC = nucleos(t)ide analogue; PBMC = peripheral blood mononuclear cell; PK = pharmacokinetic; RBR = research biosample repository; SAE = serious adverse event; scRNAseq = single-cell RNA sequencing.

- a. A period refers to the time between one dose of treatment and the start of the next. Up to 6 periods in total.
- b. If HBsAg value does not return to baseline level on Day 169 of the last treatment period, participant needs to come to the clinic for additional follow-up visits every 56 days until HBsAg value returns to < 0.1 log below baseline for two consecutive visits, or up to 56 weeks after final dose, whichever comes first.

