| ALT elevations during treatment: | 
 • If ALT elevation with preserved hepatic function (e.g., no significant changes in bilirubin, INR, PT, albumin, and/or ALP): 
 ○ ALT 3–10×ULN: Repeat ALT, LFTs (total bilirubin, direct bilirubin, AST, ALP, albumin), coagulation (INR, PT), and PD parameters (HBV DNA, HBsAg) every week until ALT < 3×ULN. ○ ALT > 10×ULN: Interrupt RO7565020 (in Part 3), and continue NUC treatment. Repeat ALT, LFTs, coagulation, and PD parameters twice weekly until ALT level < 10×ULN, then weekly until ALT < 3×ULN. Consider re-introducing RO7565020 on a case-by-case basis based on subsequent laboratory results. • If ALT elevation accompanied by declining liver synthetic and excretory functions (total bilirubin > 2×ULN, or albumin < 3.0 g/dL, or INR > 1.5) or other signs of hepatic impairment (severe fatigue, vomiting): 
 ○ Discontinue RO7565020 (in Part 3), and continue NUC treatment. ○ Repeat ALT, LFTs, coagulation, and PD parameters twice weekly until levels return towards baseline levels or normal range. ○ Investigate the participant for potential etiologies of the laboratory changes. ○ If alternative reasons/diagnoses cannot explain the laboratory changes, potential DILI will be considered. 
Notes:
 
 ○ Frequency of monitoring may need to be adjusted on the basis of clinical scenario and severity of injury. ○ As the central laboratory results generation and reporting will take time, additional local laboratory tests may be performed at the same time as the central laboratory test, and decision-making may be based on local laboratory results. ○ For marked and/or persistent ALT elevations, collect a spare serum sample (to allow retrospective evaluation of potential etiologies) and consider liver biopsy on a case-by-case basis (if deemed clinically relevant). • If ALT elevations are associated with increased HBV DNA levels, virological breakthrough will be suspected and managed as described below. |

Table 9 Guidelines for Managing Specific Adverse Events (cont.)

| Event | Action to Be Taken |
|---|--|
| For Parts 2 and 3 only (participants with CHB) (cont.) | |

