9.4.4 Immunogenicity Analyses

The immunogenicity analyses will include all participants with at least one ADA assessment, irrespective of whether or not the participant receives any treatment ([Shankar et al. 2014](#)).

The numbers and proportions of ADA-positive participants and ADA-negative participants at baseline (baseline prevalence) and after study treatment administration (post-baseline incidence during both the treatment and follow-up periods) will be summarized.

- Participants are considered to be ADA positive if they are ADA negative or have missing data at baseline but develop an ADA response following study treatment administration (treatment-induced ADA response), or if they are ADA positive at baseline and the titer of one or more post-baseline samples is at least 4-fold (e.g., ≥ 0.60 -titer units) greater than the titer of the baseline sample (treatment-enhanced ADA response).
- Treatment-induced ADA responses will be further categorized as either:
 - Transient ADA response: defined as a) ADA negative or no ADA available at baseline, and b) at least one post-treatment ADA-positive sample, and c) only one ADA-positive sample or the time between the first and last ADA-positive sample is less than 16 weeks and d) the last ADA sample is negative
 - Persistent ADA response: defined as a) ADA negative or missing data at baseline, and b) post-treatment ADA-positive samples over 16 weeks or more or the last ADA timepoint is positive ([Shankar et al. 2014](#))
- Participants are considered to be ADA negative if they are ADA negative; if they have missing data at baseline and all post-baseline samples are negative; or if they are ADA positive at baseline but do not have any post-baseline samples with a titer that is at least 4 fold greater than the titer of the baseline sample (treatment unaffected).

The relationship between ADA status and safety, efficacy, PK, and biomarker endpoints will be analyzed and reported descriptively via subgroup analyses.

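### Does the undefined treatment window in Table 11 leave the laboratory shift table without post-dose values in the single-dose parts?

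*Combined protocol and SAP*

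**What the plan says.** The laboratory row of Table 11 plans individual outputs with flags, summary tables of values and changes over time, and one display by grade: "Shifts in DAIDS grades v2.1 from baseline to the worst grade observed during treatment will be presented for selected laboratory parameters". Neither Section 9 nor the statistical notes on laboratory data in Appendix 4 says when treatment begins or ends for this display.

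Elsewhere the documents use treatment terms in more than one way.

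- Table 7 in Section 4.3 has a treatment-period column. The Part 1a row begins "Up to 28 days | Day 1 | Day -1 to Day 4", so the treatment period is Day 1. Parts 2a and 2b have the same entry. Part 1b has up to 169 days and Part 3 up to 337 days.
- Section 9.4.4 treats treatment and follow-up as two things when it describes anti-drug antibody results: "post-baseline incidence during both the treatment and follow-up periods".
- Table 9 in Section 8.3.7 has a row "ALT elevations during treatment" among its entries for Parts 2 and 3, and Part 2 is single-dose.
- The Part 1b and Part 3 schedules in Section 1.3 place every visit after the final dose under the heading "Last treatment period". Footnote b of Table 4 follows suit: "If HBsAg value does not return to baseline level on Day 169 of the last treatment period".
- Section 8.3.1 fixes the adverse event window plainly: events after the start of treatment "will be reported until the last scheduled follow-up visit".

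**The concern.** A shift table needs a baseline value and at least one later value inside the window. In Part 1a no chemistry, hematology or coagulation sample is scheduled on Day 1. In Part 2 the Day 1 sample is taken before dosing. A programmer who took the window from Table 7 would therefore find no scheduled post-dose value in either single-dose part, while one who took it as any time after dosing would find all of them. The frequency of abnormal laboratory findings is part of the primary endpoint, the antibody is engineered for a longer half-life (Section 2.2.3), and follow-up lasts 24 weeks or more. A display that dropped late worst grades would be a poor safety summary. In Parts 1b and 3, a window closing on the last dosing day would also leave out the post-treatment visits.

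**Working it through.** **Inputs.** Chemistry rows of Tables 1 to 4 (Section 1.3), with their predose footnotes; treatment periods from Table 7; the definition of a period in the Part 1b and Part 3 schedules (one dose to the next, at most 6); the dosing intervals of 28, 56 and 84 days used as examples there.

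**Single-dose parts, Table 7 reading (Day 1 only).**

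- Part 1a post-dose chemistry: Days 2, 8, 15, 21, 29, 57, 85, 141, 197, 253 = 10 visits. Inside Day 1: 0 of 10.
- Part 2 post-dose chemistry: Days 2, 8, 15, 22, 29, 57, 85, 113, 141, 169 = 10 visits. Additional visits every 56 days up to Day 393: 169 + 56k for k = 1 to 4 gives Days 225, 281, 337, 393. Inside Day 1: 0 of 10, or 0 of up to 14.

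**Single-dose parts, any time after dosing.** 10 of 10 in Part 1a; 10 of 10 in Part 2, plus up to 4. The counts behind the concern are correct.

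**Does Table 7 show that treatment ends on the last dosing day?** Last-dose day = 1 + interval × (doses − 1).

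| Part | Table 7 maximum | Window ends on last-dose day | Window ends one interval after the sixth dose |
|---|---|---|---|
| 1b | 169 | 1 + 84 × 2 = 169; 1 + 56 × 3 = 169 | 1 + 28 × 6 = 169 |
| 3 | 337 | 1 + 84 × 4 = 337 | 1 + 56 × 6 = 337 |

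Both maxima are reproduced under both readings, so Table 7 cannot decide between them.

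**What would fall outside the window in the multiple-dose parts (chemistry, days of the last period).**

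- Part 1b has 11 visits after the last dose: Days 2, 4, 8, 15, 21, 29, 57, 85, 141, 197, 253. A window closing on the last dosing day omits all 11. With six doses every 28 days and one further interval, Days 2 to 29 stay in (6 visits) and 5 are omitted.
- Part 3 has 8, as the table was extracted: Days 8, 15, 29, 57, 85, 113, 141, 169. The last-dose reading omits 8. With six doses every 56 days and one further interval, Days 8, 15, 29 and 57 stay in and 4 are omitted. Up to 4 additional visits also fall outside on either reading.

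**Which sense does the protocol use for a single-dose part?** Part 2 has no post-dose ALT scheduled on Day 1, so the ALT row of Table 9 means nothing there unless treatment runs past Day 1. The virological breakthrough row uses the same phrase. In Part 2 the first scheduled post-dose HBV DNA is on Day 85, as the table was extracted. Where the protocol applies the phrase to a single-dose part, it means the time after dosing.

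**The case for a change.** The best case for a change is that the text does admit two readings. The statistical chapter separates treatment from follow-up in 9.4.4, Section 8.11 has separate headings for assessments during treatment and at follow-up, and 8.3.1 shows how easily an end point can be written. Part 1a is the hardest case: one dose, no background therapy, and a stated treatment period of Day 1. DAIDS grades also matter elsewhere, since the Part 1 cohort stopping rules count Grade 2 laboratory abnormalities.

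The ambiguity stands; the consequence does not.

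- Table 7 sets out how long participants are in each stage of the study. It is not an analysis definition, and Section 9.4.2 does not point to it.
- The narrow reading produces a shift table with no scheduled post-baseline blood value. Such a result shows itself at the first dry run and would not pass into a report unnoticed.
- Dose-escalation decisions rest on all available safety data to at least 28 days after dosing (Section 4.1.1.1), and that section does not mention the shift table.
- The shift table is not the only place where graded laboratory results appear. Clinically significant abnormalities are recorded as adverse events (Appendix 3, Section 4), graded by DAIDS v2.1 (Appendix 2, Section 3.1), collected to the last scheduled follow-up visit and summarized by severity. That route covers only abnormalities judged to be adverse events, so it supplements the shift table without replacing it.

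**Conclusion.** No change to the plan is called for. Table 11 leaves one term undefined, and the literal Table 7 reading would take the single-dose shift tables from 10 scheduled post-dose visits to 0 in each part. That reading defeats the purpose of the table and conflicts with how Section 8.3.7 uses the term for Part 2. An analyst would count values after first dosing, with the adverse event window in 8.3.1 as the obvious end point. For Parts 1b and 3 the end day is open, and the number of chemistry visits at stake depends on the regimen and the reading: 11 or 5 in Part 1b and 8 or 4 in Part 3 in the cases worked above.

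Whatever window is used, no data are lost. Individual listings with H/L and HH/LL labels, summaries over time and adverse event reporting all extend into follow-up. The study tests no hypothesis (Section 9.1), so no error rate or decision threshold depends on this table. The conclusion assumes that the table is checked against the visit schedule when it is programmed, and that the extracted schedule tables show the true visit pattern; the Part 3 rows are the least certain, since chemistry reads 8 visits after the last dose and hematology 9.
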